3. Following completion of the MRS protocol, subjects will be provided parking and discharged.

Note: Visit 3B is an optional visit. Subjects who choose to do the right heart catheterization visits will need to have blood drawn for a basic metabolic panel, PT/INR, and CBC/diff/platelets, preceding Visit 3B by no longer than 30 days, per the UPMC Cath. Lab protocol. We will coordinate this draw at one of the study or if the subjects have bloodwork prescribed for their ongoing medical care. Subjects will be provided parking for the blood draw visit, if it requires a separate visit.

Visit 3B

This visit will be completed by the subjects in the recruited sample who have consented to invasive cardiopulmonary exercise testing (iCPET). Subjects may decline this portion of the testing at consent. This fasting visit will take place in the UPMC Presbyterian Cardiac Catheterization lab (Cath. Lab) within 5 ± 2 days from Visit 3A and last approximately 4-6 hours. Subjects with diabetes will receive advisement on issues related to blood sugar management per the standardized pre-catheterization protocol of the UPMC Cath. Lab. Subjects on warfarin or NOACs will be reminded by study staff to hold those medications 3 days prior and including the day of the catheterization.

Upon arrival in the Cath. Lab, subjects will undergo:

1. Collection of adverse events, interval history, measurement of BP and other vital signs (temperature, pulse, RR, HR, SpO₂), as well as completing a breathing test, called [spirometry](#), that assess subjects ability to breathe in and out. We will confirm appropriate medications were held per individual case.
2. Brief physical exam
3. Right heart catheterization

[name], Co-Investigator, or a qualified pulmonologist or cardiologist investigator will lead the UPMC protocol for right heart catheterization, with strict adherence for safety and sterile conditions as indicated, including the use of fluoroscopy to guide the catheter placement. PA (internal jugular approach) and radial artery catheters are placed. Systemic and PA pressures (PAP) are measured continuously during exercise provocation (described below). PCWP is measured at baseline and each minute thereafter. End-expiratory assessments of right atrial pressure (RAP), RV pressure, PAP, and PCWP are assessed.

Approximately 2 ml blood samples are drawn from the radial and PA catheters during rest and the last 15 seconds every other minute of exercise for measurement of blood gases (PA blood gas will be used for assessments of Qt and peripheral blood gas for assessment of systemic O₂ extraction i.e., PA oxygen (Ca) minus venous oxygen (vO₂), as well as for pH and lactate. Systemic and pulmonary arterial blood are analyzed at 37°C for partial pressures of O₂ and CO₂ (PO₂, PCO₂), pH, hemoglobin (Hb), and O₂ saturation. Blood O₂ content is calculated from Hb and O₂ saturation: $S(a)O_2 \times Hb \times 1.34$. The Fick principle is used to calculate Qt (i.e., $Qt = VO_2 / (Ca - vO_2)$) during exercise. Predicted cardiac output (Qtmax) is calculated from the predicted VO₂ max assuming a normal maximum exercise arterial-mixed venous O₂ content difference (Ca-vO₂) and Hb of 14 g/dL. The pulmonary vascular resistance (PVR) is calculated from $(PAP - PCWP) / Qt$. RPE and ratings of dyspnea are assessed during iCPET and analyzed in relation to simultaneously collected lactic acid levels as a further assessment of skeletal muscle metabolism underlying fatigability⁸⁴. Furthermore, these relationships will be assessed in relation to concurrent ventilatory dynamics (VO₂, VE/VCO₂,

and RER) as determined by concurrent CPET. The total blood volume will depend on the total time exercising but is likely not more than approximately 32 ml (2 ml at baseline and 2 ml per minute of exercise, maximum likely 15 minutes, from radial and pulmonary arteries)

Cardiopulmonary Stress Exercise Testing to be performed during the right heart catheterization (invasive CPET): Maximal graded exercise testing will be conducted in association with air-gas-exchange during the right heart catheterization. A qualified pulmonologist or cardiologist will be available throughout the exercise provocation. A computerized cycle ergometer using a ramp protocol will be used to generate a symptom-limited exercise stimulus. A lightweight disposable pneumotach device face mask will be positioned over a subject's mouth and nose during the exercise for gas exchange assessments; VO_2 , VE/VCO_2 slope, and respiratory exchange ratio (RER) are ventilatory parameters that will be measured during exercise. Simultaneously, intra-cardiac assessments of pulmonary wedge pressure, right heart pressures, and cardiac output will be determined by the pulmonary arterial catheter. HR and BP, time, and ECG waveforms will also be assessed. Any unexpected abnormalities will be reported to the patient's cardiologist or primary care physician; continued participation in the study will require physician clearance. Subjects will be asked for ratings of exertion and shortness of breath during the testing. ACSM criteria for starting and stopping will also be utilized.

iCPET may be completed in combination with echocardiography depending on the quality of baseline images. Echocardiographic images may be obtained at rest at baseline, and then every 2 minutes during exercise and immediately post-exercise. Quantitative echo measures of LV size, and systolic and diastolic function are made at rest and exercise. Lusitropy is assessed based on the calculation of left ventricular end-diastolic volume (LVEDV) divided by PCWP. The net effect on cardiac function is a Starling curve, i.e., $SV/LVEDV$ at rest and with exercise.⁸⁴

4. Following completion of the testing, subjects will have catheters removed and monitoring for about 2 hours post-test. They will be given any needed education for post catheterization, including site care and resuming anti-coagulant or anti-diabetic medications that were held for the procedure. Prior to discharge, they will be confirmed medically stable by a study physician. Subjects will be provided a meal.

Visit 4

Subjects will be scheduled for an outpatient visit at the University of Pittsburgh CTSC in UPMC Montefiore within 10 days \pm 4 days from Visit 3A for subjects who did not complete iCPET or within 5 days \pm 2 days from Visit 3B for those who did complete iCPET.

Subjects will be asked to observe 8 hours fasting prior to arrival. Upon arrival subjects will be served a limited standardized breakfast.

This visit will last approximately 4-5 hours. To prevent acute effects of exercise on muscle mitochondrial function, this visit will occur no earlier than 2 days after Visit 3A/3B. Prior to the biopsy, study staff will call indicated subjects to hold their anti-platelet and anti-coagulation medications for 1-5 days (depending on the different medications and relative half-lives, as approved by their cardiologist). Subjects with diabetes who are on hypoglycemic medications will be advised if they need any adjustment to their usual regimen.

While the standardized breakfast is being prepared, subjects will undergo:

1. Interval history, measurement of BP and other vital signs (temperature, HR, body weight, RR, and SpO_2)

2. Staff will also confirm subject is fasting and that the anti-coagulation regimen was withheld as prescribed. Nursing will place an IV line.
3. A study physician will perform a brief physical exam.

4. Skeletal Muscle Biopsies

An important component of the protocol is the muscle biopsy. Subjects who refuse biopsy will not be enrolled. However, participants who complete the first biopsy and then state (prior to being given drug) that they will not complete a second biopsy at Visit 7 will be withdrawn from the study. Alternatively, patients who refuse the 2nd biopsy after they have completed the 4 weeks of NO₂/placebo therapy will still complete the other post drug assessments. If other unique subject situations arise, they will be evaluated by the PI and a decision will be made with regard to completing the other post assessments or not (e.g., completion of 2 weeks on drug, and then refusal to complete biopsy.)

For the biopsy, patients will lie comfortably in the supine position for biopsy of the vastus lateralis muscle of the non-dominant leg. Biopsy sites will be prepped with chlorhexidine. Lidocaine will then be administered, superficially initially and then more deeply into the muscle, using a small gauge needle. Subjects who report a history of poor pain control or low threshold will be offered the use of a topical anesthetic cream prior to the lidocaine. Ultrasound may be used to enhance visualization of the site for the needle insertion. A small superficial incision will next be completed using a #11 blade scalpel. A 5 mm Bergstrom muscle biopsy needle will be inserted through the skin incision and advanced into the muscle. Suction will be generated using a syringe attached to the outside portion of the needle, to thereby suck skeletal muscle into a hole on the side of the needle positioned in the muscle tissue; this draws a small piece of muscle tissue (about 150 mg of muscle tissue) into the hollow shaft of the needle, which is then cut with a cutting trocar that slides through the shaft to cut the tissue drawn within its core. After harvesting the first sample, the needle will be rotated 90 degrees, and a second sample extracted to maximize yield for analysis. Additional passes of the needle may be necessary for an adequate muscle sample. The wound site will be closed with steri-strips and a sterile pressure bandage.

Muscle specimens will be immediately processed, and stored. Muscle specimens are divided into portions. Fragment 1 is immediately frozen in liquid nitrogen in preparation for polymerase chain reaction (PCR) analysis for DNA /RNA isolation, protein homogenates used for enzymatic assays and Western analysis. Fragment 2 has the muscle fibers aligned for microscopy, placed in OCT, then cooled in a thawing isopentane slurry and placed in a cryotube and frozen in liquid nitrogen for histochemistry. Fragment 3 is prepared for electron microscopy. Fragment 4 is processed in the CTCRC and EMRC immediately for bioenergetics analysis. Any extra tissue will be stored for future analyses.

Subjects will rest for approximately 30 minutes post biopsy while wound is compressed and dressed and prior to baseline vitals prior to dosing. Study staff will record a baseline level of symptoms, i.e., dizziness, lightheadedness, etc. for use during weekly phone calls, prior to dosing.

5. Research bloods

After the standardized meal is completed, a blood sample via IV line will be drawn for inflammatory peptides (IL-1, IL-6, IL-15, TNF α), adipokines (leptin and adiponectin) vitamin D, GFR, BNP or NT-pro BNP, TSH, HbA1c. Samples for platelets and NO₂ levels will also be drawn at baseline into a 1) heparinized syringe and 2) a cell preparation tube (CPT). Additional collection of NO₂ levels will be drawn at 30 minutes, 60 minutes and 120 minutes.

Heparinized blood will be immediately centrifuged at bedside to separate plasma and red cells and then flash frozen for later NO₂ measurements (via reductive chemiluminescence to determine that NO₂ levels were increased in the muscle as described. The second tube of blood (CP tube) will be immediately subjected to differential centrifugation in order to isolate platelets. Platelet bioenergetics will then be measured via the Seahorse Extracellular Flux Analyzer including basal, non-ATP producing, maximal and non-mitochondrial respiratory rates along with glycolytic rate. If subjects have had an HgbA1c, TSH or vitamin D level within approximately 3 months, or a BNP or GFR within approximately 1 month, (all per physician discretion), we may defer this blood draw.

Extra aliquots will be stored for use in future studies. Total volume of blood drawn will be about 72 ml (about 4.9 tablespoons).

6. pK

CTRC nursing staff will measure BP, RR, HR, SpO₂ and MetHb to ensure they are at a SS before administering the study drug/placebo (baseline). Subjects who are 80 years of age or older or <80 with risk factors for hypotension will receive 20 mg drug/placebo; all others will receive 40 mg drug/placebo. Subjects will receive their first dose of study drug/placebo as follows: 14N sodium NO₂/placebo, from their day 1, AM dose, week 1 pill box, strength 20 or 40 mg dependent upon parameters described in section "Study Design", p. 6. Then, the following will be assessed: BP (sitting and then standing after 3 minutes), HR and MetHb, RR and SpO₂ every 15 minutes for the 2 hours post-drug administration period. If subjects experience high methemoglobin level, hypotension or symptoms, the PI will be informed and advise on plan for dosage or other management. See Dose Selection, subsection, Dose Reduction).

7. Drug distribution

Subjects will receive sufficient study drug/placebo supply to cover the period up to the next scheduled visit at Visit 5 and/or through Visit 7 as needed. We will instruct subjects to return all of the study drug packaging, including unused study drug and empty packaging at each study visit and/or at the time of discontinuation from treatment.

Study staff will review medication administration and use of the drug diary card with all subjects. Subjects will be asked to record the time they take the drug each day and any symptoms with severity rating and/or health events during the dosing period.

The study staff and/or CTRC RN will review biopsy site care with subjects and if indicated, remind subjects to resume their normal anti-coagulation/anti-platelet/anti-diabetic medications.

The subject will receive payment for visits 1-4 and can then be discharged.

Drug Dosing Period and Outpatient Monitoring

Subjects will then complete no less than 28 (-3) days on drug. Subjects will continue on drug/placebo through the post testing period; the duration will vary with the visit windows and if subjects are doing both 6A and 6B. During the 28-day period, subjects will be called on a weekly basis by study staff, beginning on the visit 4 day plus 7 days \pm 2 days, and continuing approximately weekly thereafter. Study staff will query subjects on any symptoms, home BP readings if applicable, health care, including medication changes, or adverse events, and compliance with study drug/placebo regimen. Any AEs or medical issues of concern will be promptly communicated to the PI or covering study physician by email or phone depending on urgency; and AEs will be documented in the study log which is reviewed with PI at least bi-

weekly. Subjects will be again reminded to communicate any medication changes prescribed by their health care team to study staff as soon as possible, not to wait for the weekly call. (Serious adverse events will be reported as described in Section 6.4.5.) Management of hypotension or methemoglobinemia related symptomatology will be as described in 2.3.3 Dose Selection, subsection Dose Reduction.

Post Assessments (continuing on NO₂/placebo tid)

Visit 5

This visit will be scheduled 28 ±3 days from Visit 4, take place in the UPMC Montefiore EMRC and/or Pepper SMART Center and include all of the Functional testing described in Visit 2.

1. Upon arrival subjects will have measurement of BP, temperature, RR, HR, SpO₂ and MetHb and body weight. Study staff will check for interval history, adverse events, and complete a symptom assessment. The drug diary cards and empty drug boxes for completed weeks on study drug/placebo will be collected. Medication compliance will be reviewed. A study physician will perform a brief physical exam.
Physical Function Battery
 - a. nCPET
 - b. Fatigability assessment on treadmill (SS).
 - c. Self-determined walking (6MWT)
 - d. NIRS will be collected during the nCPET, SS and 6MWT.
 - e. Short Physical Performance Battery (SPPB).
 - f. Participants again will be asked to wear the Actigraph during the post-intervention nCPET treadmill, 6MWT and steady-state treadmill. After testing, subjects will wear the ActiGraph for one week and complete a physical activity/sleep diary for days wearing the device.
 - g. Hand Grip Strength Assessment
2. The same questionnaires as at Visit 2 will be administered interspersed with functional testing.
3. Subjects will be asked to complete another 3DFR as per Visit 2.
4. Prior to discharge, subjects will be reminded to return the ActiGraph and 3DFR at visit 6A or 6B, depending on testing schedule.

If study team or subject feel as though any of the study procedures at this visit are not safe and/or would be too burdensome to the subject, subject may not complete all of the procedures at this visit.

Visit 6A

This visit will replicate the ³¹P Magnetic Resonance Spectroscopy protocol described at Visit 3A. The same safety precautions will be followed. This visit will be scheduled within 5 ±2 days of Visit 5. Following this visit, the subject will advance to either Visit 6B or 7 depending if consented to the iCPET. Pre- catheterization labs will be drawn as described per Visit 3A.

1. Upon arrival subjects will have interval history and measurement of BP, temperature, RR, HR, SpO₂, and MetHb. Study staff will check for interval history, adverse events, and complete a symptom assessment. The drug diary cards and empty drug boxes for completed weeks on study drug/placebo will be collected. Medication compliance will be reviewed.
2. Any concern for medical instability after vitals and interval history are collected will prompt contact with a study physician, and possible physical exam clearing to proceed.
3. If completion dates have passed, the 3DFR issued at Visit 5 will be reviewed with the subject for clarification and completion.

Visit 6B

This visit will replicate the iCPET testing described in visit 3B for those subjects who elected to participate. This visit will be scheduled within 5 ±2 days of Visit 6A. The same safety protocol and procedures will be followed as in 3B. This visit will be completed by the subjects in the recruited sample who have consented to iCPET, Visit 3A. This fasting visit will take place in the UPMC Presbyterian Cardiac Catheterization lab and last approximately 4-6 hours. Subjects with diabetes who are on hypoglycemic medications will be advised on medications to hold the day before and morning of visit.

iCPET

Upon arrival in the Cath. Lab, subjects will undergo:

1. Collection of adverse events, interval history, measurement of BP and other vital signs (temperature, pulse, RR, HR, SpO₂ and MetHb) and symptom assessment.
2. Brief physical exam
3. UPMC protocol for right heart catheterization will be followed, with strict adherence for safety and sterile conditions as indicated. PA (internal jugular approach) and radial artery catheters are placed as described in 3B. Volume of blood as noted approximately 32 ml, maximum.
4. Following catheterization, subjects will have catheters removed and be given any needed education for post catheterization site care. They will be confirmed medically stable by a physician, before leaving. Subjects will be provided a meal.

Subjects will return their Actigraph and diary at this visit, or Visit 7 if they do not complete Visit 6B with heart catheterization.

Visit 7 (Completion Visit to be scheduled 10 days ±4 days for subjects only doing visit 6A or 5±2 days following Visit 6B).

This visit will be at UPMC Montefiore CTSC and will replicate the blood draw and muscle biopsy procedures described in Visit 4. The same precautions and procedures will be followed including reminding, withholding, and confirming of the anti-coagulant/anti-diabetic regimen per subject. Subjects will take their last morning dose of study drug/placebo on the day of the visit. Subjects will be asked to observe 8 hours fasting prior to arrival. Upon arrival subjects will be served a limited standardized breakfast. Confirmation of last dose will be completed with subjects at the visit.. This visit will last approximately 2 hours.

1. While the standardized breakfast is being prepared, interval history/AEs and temperature, RR, BP, HR, SpO₂, MetHb, body weight, and symptom assessment will be collected. A brief physical exam will be completed. The Canadian Clinical Frailty Scale will be repeated.
2. Medication compliance via drug diary cards, empty pill box compartments, and subject report will be assessed. Unused capsules will be counted and returned to IDS following the visit.
3. The 3DFR issued at Visit 5 will be reviewed with the subject for clarification and completion.
4. ActiGraph and diary will be collected if not at previous visit
5. Blood draw to include: Inflammatory peptides (IL-1, IL-6, IL-15, TNFα), adipokines (leptin, adiponectin). GFR, BNP or NT-pro BNP, platelet sample and NO₂ levels. Additional NO₂ levels will be drawn at 30 minutes, 60 minutes and 120 minutes. Total volume of blood drawn will be about 64 ml (about 4.3 tablespoons). If subjects have had BNP or GFR within approximately the last month via their clinical care, the study physician can defer this blood draw.
6. Skeletal Muscle Biopsies: same as described in Visit 3.
7. Transthoracic Echocardiogram. The subject may be transported to a UPMC Presbyterian/Montefiore lab for an echocardiogram.

Following the echocardiogram subjects will be discharged. They will receive payment for visits 5-7 and study drug period.

End of Trial and Follow-Up Period

Post Study drug/placebo Telephone Assessment (about 7 days following Visit 7)

- Telephone assessment for interval histories, muscle biopsy follow up and AEs will be completed. Any remaining symptoms or AEs which are suspected to be related to the study drug/placebo will be evaluated by [name] and follow-up plan for care devised as needed.

Table.2.2.1 Study Visits and Assessments		
Phase	Visit	Assessments and Procedures
Screening	Visit 1	Informed consent and physical exam; Hgb* Home accelerometry; Echo†; issue 3DFR, frailty assessment
Pre- Assessment Series	Visit 2 (within 28 days of Visit 1)	Non-invasive functional assessment battery: Symptom-limited nCPET; Fatigability assessments (perceived [SS] and performance [6MWT]), NIRS during nCPET, SS, 6MWT, Accelerometry during nCPET, SS, 6MWT and 1 week at home with diary; Hand grip, SPPB, Questionnaires
	Visit 3A (5 days ±2 days from V2)	³¹ P MRS protocol; review 3DFR and return ActiGraph 3A or 3B per dates; pre-cath bloodwork if applicable
	Visit 3B (5 days ±2 days from V3A)	Symptom limited iCPET with associated exercise echocardiography
	Visit 4 (10 days ±4 days from V3A or 5 days ±2 days from V3B)	Research bloods**; Skeletal muscle biopsy; Administration of first dose of NO ₂ ; PK assessment and BP assessment; Drug distribution
Drug dosing	Weekly phone calls	Phone call monitoring of drug tolerance, symptom assessment, medication compliance, adverse events.
Post-Assessment Series	Visit 5 (28 ±3 days from Visit 4)	Non-invasive functional assessment battery: Symptom-limited nCPET; Fatigability assessments (perceived [SS] and performance [6MWT]), NIRS during nCPET, SS, 6MWT, accelerometry during nCPET, SS, 6MWT and 1 week at home with diary; Hand grip, SPPB, Questionnaires; issue 3DFR
	Visit 6A (5 days ±2 days from V5)	³¹ P MRS protocol; review 3DFR and return ActiGraph 6A or 6B per dates; pre-cath bloodwork if applicable
	Visit 6B (5 days ±2 days from V6A)	Symptom limited iCPET with associated exercise echocardiography
	Visit 7 (10 days ±4 days from V6A or 5 days ±2 days from V6B)	Frailty assessment, Skeletal muscle biopsy; Research bloods‡; echo after meal

*Unless Hgb within normal limits recently prior to Visit 1 and deferred by physician; †deferred if recent per physician discretion;

**Platelets, nitrite/nitrates (time 0), + nitrites/nitrates (time 30 mins, 60 mins, and 120 mins); inflammatory peptides (IL-1, IL-6, IL-15, TNFα); adipokines (leptin, adiponectin); vitamin D, GFR, BNP or NT-pro BNP, TSH, HgA1C (unless recently measured)

‡Platelets, nitrite/nitrates; inflammatory peptides (IL-1, IL-6, IL-15, TNFα); adipokines (leptin, adiponectin); BNP, GFR, unless recently measured

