The PI, [name] has an ongoing pilot study of oral NO₂ 40 mg tid with healthy controls, HFpEF and HFrEF subjects. Ten control subjects have completed the pilot without any significant product related adverse events. Mild and transient symptoms consistent with what other investigators have observed have been present in some of the other subjects.

Experience thus far in the pilot with heart failure subjects has suggested a tendency for a vasoactive response to nitrite not seen in the controls. Subjects with both HFrEF and HFpEF enrolled thus far have all required dose reductions to 20 mg tid to prevent hypotension. Thus we have adopted the stratified dosing as described for this protocol.

As the pilot is ongoing, data is incomplete. One preliminary analysis has been completed. In assessments of the 5 healthy controls, needle point data show 1 month of NO_2 at 40 mg tid achieved reduced VO_2 at the same submaximal workloads (Figure 3a), reduced VE/VCO_2 (Figure 3b) slopes at SS workloads, and significantly improved post-exercise recovery dynamics (Figure 3c)

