2. Medical history obtained prior to the visit will be reviewed with subject. Subjects will be asked questions about any heart disease and related diseases in first degree relatives; no identifying information will be obtained. History and physical examination. [name] or study physician will evaluate subjects 70-<80 years of age for risk of hypotension and need for dose reduction. The study physician will also complete the Canadian Clinical Frailty Scale. Subjects will be reminded to inform study staff as soon as possible of any health or medication changes while they are in the study.
3. Body weight and height. BP and other vital signs [temperature, pulse, respiratory rate (RR), HR, SpO₂]. BP may be re-measured once if out of inclusion range. This is to allow for influences of medication activation, subject nervousness, lack of fluid intake, and known factors which contribute to clinical variation.
Screening evaluation will include a hemoglobin and hematocrit (H/H) by the UPMC Presbyterian clinical automated testing lab and are to be covered by research funds. The total volume of blood drawn is approximately 1 teaspoon (4 mL). If subjects have a recent hemoglobin value, the physician will determine if this blood draw can be deferred.
4. Subjects will be issued an ActiGraph GT3X+, non-invasive wrist monitoring device to be worn for a full 7 days during the first and approximately 9th weeks of the study to assess changes in daily activity, level/intensity and sleep. Subjects will receive instruction in the use of the

- ActiGraphs and complete a physical activity/sleep diary for days wearing the device. Subjects will be reminded to return their ActiGraph at Visit 2/3A.
5. Transthoracic Echocardiogram (performed by trained study staff). If subjects have had a recent echocardiogram, the records will be obtained prior to visit one and the test results will be reviewed and interpreted by a study physician in lieu of performing one. A trained sonographer will obtain the echocardiogram and a cardiology attending will be responsible for interpretation. The subject may be transported to a lab in the UPMC Presbyterian/Montefiore system for the echocardiogram.
 6. Subjects will be instructed in and provided forms to complete a three-day food record (3DFR) to observe subject's dietary intake.

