We will ask participants to complete them interspersed among the physical function tests so as to reduce fatigue of both assessments.

The 3DFR issued at Visit 1 will be reviewed with the subject for clarification and completion as well as the ActiGraph diary.

Prior to departing, we will remind subjects to resume their usual medication regimen if changes were made with regard to diabetes.

If study team or subject feel as though any of the study procedures at this visit are not safe and/or would be too burdensome to the subject, subject may not complete all of the procedures at this visit.

Visit 3A

Subjects will be scheduled for an outpatient visit at the University of Pittsburgh Magnetic Resonance Research Center (MRRC) in UPMC Presbyterian 5±2 days from Visit 2. This is a non-fasting visit (patients will be asked to eat a light meal) and will last approximately 2-3 hours. Subjects who are identified to have the presence of metal or non-MRI compatible device will not complete Visit 3A (or 6A).

Subjects will undergo:

1. Collection of interval history, measurement of BP and other vital signs (temperature, pulse, RR, HR, SpO₂) by study or MRRC staff.
Any concern for medical instability after vitals and interval history are collected will prompt contact with a study physician, and possible physical exam before proceeding.
2. The study coordinator will clear the subject as safe for MRI prior to the enrollment. Then the safety protocol and procedures of the MRRC will be followed as well as a double check for safety. The MRS is an in-vivo test to measure maximal mitochondrial capacity to generate ATP. It will be performed on the subject's leg as they complete a flexion-extension exercise within the bore of the magnet as described below.

Prior to the exercise, the technician will collect a fully-relaxed (FRS), high resolution ³¹P spectrum of the resting muscle. Then the exercise protocol will be performed: Participants lay supine with the non-dominant knee (unless contraindicated) elevated at ~30° and straps are placed over the legs. Participants perform voluntary isometric contractions (kicking) repeatedly as hard and as fast as they can for two bouts each followed by a rest period. The protocol is designed to deplete PCr stores by 33-66% to ensure high signal to noise defining PCr recovery without inducing acidosis (pH <6.8), which inhibits oxidative phosphorylation.

82, 83

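### By the visit text, home actigraphy normally precedes the exercise battery at baseline but follows it at follow-up, and Table 2.2.1 contradicts the baseline timing; both weeks should sit at the same position relative to testing

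*Combined protocol and SAP*

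**What the plan says.** **Baseline, visit text.** Section 2.2, Visit 1, item 4 issues the device "to be worn for a full 7 days during the first and approximately 9th weeks of the study". It then states: "Subjects will be reminded to return their ActiGraph at Visit 2/3A". At Visit 2 the diary is checked: "The 3DFR issued at Visit 1 will be reviewed with the subject for clarification and completion as well as the ActiGraph diary". Visit 2 must fall within 28 days of Visit 1; no minimum gap is given.

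**Baseline, table.** Table 2.2.1 lists home accelerometry in the Visit 1 row. Its Visit 2 row, which holds the exercise battery, also has "Accelerometry during nCPET, SS, 6MWT and 1 week at home with diary". It puts device return at Visit 3A or 3B.

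**Follow-up.** Visit 5, item f, begins home wear once the battery is done: "After testing, subjects will wear the ActiGraph for one week". The battery comprises a symptom-limited nCPET, the 5-minute treadmill walk and the 6MWT. The table then schedules "Visit 6A (5 days ±2 days from V5". Visit 6A repeats the Visit 3A spectroscopy, with two bouts of all-out kicking. Visit 6B, the optional iCPET, comes 5 ±2 days after 6A. The Visit 5 text has the device returned at 6A or 6B; the Visit 6B text says 6B or Visit 7.

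**Use of the data.** The second Aim 1 hypothesis links lower fatigability to higher daily activity. Section 2.5.3 compares arms on change adjusted for baseline, counts displays of individual change as support for the Aim 1 hypotheses, and for Aim 2 correlates changes both pooled and within arm.

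**The concern.** A change score is interpretable as change in habitual activity only if the two recordings are made under like conditions. On the visit text they are not: the baseline week normally contains no study exercise, while the follow-up week opens after a maximal test and, for most participants' schedules, contains at least one further study visit. Any rest taken after testing, or any unusual activity on a visit day, then enters the follow-up week only. The table points to a different baseline week, so some participants could be recorded before the battery and others after it. What is at stake is whether the activity hypothesis is answered from free-living activity or partly from the visit schedule.

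**Working it through.** **1. The plan's own figure.** The only number attached to the follow-up week is that it falls in about study week 9. Take Visit 1 as day 0 and nominal gaps: Visit 2 to 3A 5 days, 3A to Visit 4 10 days, Visit 4 to Visit 5 28 days. With Visit 2 on day 14 (an assumption), Visit 5 = 14 + 5 + 10 + 28 = day 57, which is week 9. With Visit 2 on day 7 it is day 50 (week 8); on day 28 it is day 71 (week 11). The stated week is therefore consistent with wear starting at Visit 5.

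**2. What falls inside the follow-up week (Visit 5 = day 0).**
- Visit 6A: 5 ±2, so days 3 to 7, always within the 7 days for those who attend. Participants with metal or an incompatible device skip 3A and 6A.
- Visit 6B: (3 to 7) + (3 to 7) = days 6 to 14. It falls on day 7 or earlier only for the gap pairs 3+3, 3+4 and 4+3, which is 3 of 25 combinations, and only in those who chose iCPET.
- Return of the device at 6A leaves 3 to 7 days since Visit 5, fewer than seven unless 6A is on day 7.

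**3. What falls inside the baseline week.** A week begun at Visit 1 is clear of the battery only if Visit 2 is on about day 7 or later. With Visit 2 on day 5, 2 of 7 wear days follow the battery; on day 3, 4 of 7 do. If instead the table's Visit 2 row is followed, wear comes after the battery and spans 3A, which matches follow-up.

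**4. Effect on each planned analysis.** Write a participant's activity change as *h* + *s*, where *h* is change in habitual activity and *s* is the part due to testing and visit days.
- *Between arms:* the difference in mean change is (h_T − h_P) + (s_T − s_P). If *s* has the same mean in both arms, the second term is zero.
- *Within arm and individual plots:* *s* is carried in full.
- A simulation with 9 per arm, unit SD and no drug effect agrees. A common shift of −0.5 SD gave a within-arm mean change of −0.498 and an arm difference of 0.002; a shift of −1 SD gave −0.996 and 0.003.
- *Correlation with fatigability change F:* Cov(h + s, F) = Cov(h, F) + Cov(s, F). A constant *s* changes nothing. If *s* varies independently of *F*, it adds noise and weakens the correlation. If *s* depends on fatigability, it biases it. Section 1.4 itself says that highly fatigable people cut back activity, so this dependence is plausible.

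**5. Size.** The documents give no figure for how much activity changes on a test or visit day. For scale only: if *k* of 7 days each change by a fraction *d*, the weekly mean moves by k × d / 7. With *d* assumed at 20% to 50%, in either direction, this is 2.9% to 7.1% for k = 1, 5.7% to 14.3% for k = 2, and 8.6% to 21.4% for k = 3. Both *d* and *k* are assumptions.

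**The case against.** The strongest reply is randomisation. Both arms follow the same schedule, so a common effect drops out of the Aim 1 contrast. That stands, and it protects the main comparison.

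A reader might go further and infer that the arm contrast measures recovery, because the pilot reports "significantly improved post-exercise recovery dynamics (Figure 3c" on nitrite. The documents do not support this. The pilot statement is a preliminary analysis of 5 healthy controls at 40 mg tid, reported without a placebo comparison, alongside submaximal gas-exchange results. It says nothing about home activity over days or about HFpEF. The section on subject burden also expects participants to return to baseline between tests within a visit.

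A reader might also take it as settled that the baseline week is free of testing. It is not. The Visit 2 row of the table, and the missing minimum gap between Visits 1 and 2, leave that open. But the table does not rescue the plan either: return as early as Visit 2 and diary review at Visit 2 make little sense if wear starts after Visit 2.

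Three further points have weight. The outcome is one of many secondary ones in an 18-person pilot. The diary and raw accelerometry would allow visit days to be identified and left out, although the plan does not say that this will be done. And wear started by staff at Visit 5 may be more reliable than wear started at home.

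**Conclusion.** The point holds as an inconsistency with a probable asymmetry. On the visit text, baseline wear normally precedes testing and follow-up wear starts straight after it; the table disagrees about baseline, so timing may differ between participants. Within-arm change and the individual-change plots absorb any resulting shift, and variation in post-test activity between participants can distort the change correlations used for the activity hypothesis.

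The between-arm contrast is unaffected unless nitrite alters post-test recovery, which is possible but not shown. No size can be derived from the documents: the percentages above illustrate scale under assumed inputs and are not an estimate. The conclusion rests on reading the visit windows as days 3 to 7 and on activity differing at all after testing or on visit days. It concerns a named secondary hypothesis, not the primary RPE outcome, and merits correction mainly because correction is cheap.

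**What to change.** Reconcile the wear and return instructions in the text for Visits 1, 2, 5 and 6B and in Table 2.2.1, and place both home weeks at the same position relative to the battery. Either option works:

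- **(a) Before the battery.** Wear in the 7 days before Visit 2 and the 7 days before Visit 5. Require Visit 2 to be at least 7 days after Visit 1. Hand out the device at Visit 4, remind at the week-3 call and collect at Visit 5. Only phone calls are routinely scheduled between Visits 4 and 5. Since Visit 5 falls on days 25 to 31 after Visit 4, wear must start on days 18 to 24, so the reminder has to come earlier than a nominal day-21 call when Visit 5 is booked before day 28.
- **(b) After the battery.** Start both weeks after the battery, at Visit 2 and Visit 5, with return only once 7 days are complete. For participants who attend 3A, Visit 4 comes no earlier than day 9 after Visit 2 (3 + 6, or 3 + 3 + 3 with iCPET), so the baseline week can finish before the first dose.

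Update to match: the week-9 wording at Visit 1, Visit 5 item f, the device-return instructions, and the Visit 2, 3A, 5 and 6A rows of the table.

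The cost is protocol wording and device logistics; no visit, test or participant is added. Under (a), devices are out longer and participants start wear themselves after a reminder. Under (b), both weeks contain study-visit days.
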